3 STUDY POPULATION

The study population will include healthy adult men and women ages 18 to 45 years, inclusive. Participants will be recruited from the local Baltimore-Washington DC population through established methods, to include: future-contact authorized CVD volunteer database, local advertisements, campus flyers, and word-of-mouth. Potential volunteers who are interested in the study are instructed to call the CVD to receive further information about the study.

The process of informed consent begins when a person contacts the CVD for information about the study. CVD research staff receive these inquiries and read through an IRB-approved telephone script which describes basic information on the study topic, duration and number of visits, procedures, and eligibility criteria. No personal health information is solicited and afterwards interested potential participants are given an appointment to attend an *Orientation Session* for formal screening.

At the *Orientation Session*, the consent process continues. CVD research staff provide a detailed description of all aspects of the study, including the rationale and background, the public health significance, the procedures and schedule of visits, and a detailed discussion of the risks and the presence or absence of benefit to them, as appropriate. The prospective subject is given a copy the study consent form (without the signature page) and is encouraged to discuss his/her participation with family members or advisors before agreeing to sign the informed consent form and proceeding with any screening procedures. An interested volunteer may decide to participate in the study on a separate visit or may continue the consent process after the *Orientation Session* is completed.

A similar process of recruitment, pre-screening, and consenting process will be performed at Pharmaron. Pharmaron will use their recruitment process which may include participants outside of the local Baltimore-Washington vicinity. Pharmaron will use their established methods of recruitment which will include their volunteer database, local advertisements, social media, and other methods. As part of the consenting process, Pharmaron research staff will provide detailed description of all aspects of the study, including rationale and background, the public health significance, the procedures and schedule of visits, and a detailed discussion of the risks and the presence or absence of benefit to them. The recruitment materials will be UMB IRB approved.

Once both the investigator and the volunteer are satisfied that all questions have been answered and the volunteer expresses the desire to participate, the volunteer will be allowed to sign the consent form. A copy of the signed consent document will be given to the participant.

After the informed consent form is signed, a one-on-one private meeting with a member of the study team is performed, to continue the process of informed consent. A brief written examination is administered to assess the volunteer's comprehension of the study (i.e., *Comprehension Assessment Tool*). A passing score of $\geq 70\%$ is required; wrong answers will be reviewed with the volunteer and examination may be re-taken once. Upon successful completion of the *Comprehension Assessment Tool*, the research staff can proceed with formal screening.

3.1 Inclusion Criteria

Subjects must meet all inclusion criteria in order to participate in the study:

1. Ability to provide written informed consent
2. Age 18 - 45 years, inclusive
3. Good general health as determined by: vital signs (heart rate <100 bpm; blood pressure systolic >90 mm Hg and ≤150 mm Hg; diastolic >45 mm Hg and ≤90 mm Hg; oral temperature <100.4°F), medical history, and a physical examination[†] within 45 days before administration of first dose of vaccine.

[†] *The intent is to evaluate for acute or ongoing chronic medical conditions which have been present for 90 days or more and which could affect the assess of safety or immunogenicity. Chronic medical conditions should be stable for at least 60 days; defined as no hospitalizations, ER, or urgent care for medical intervention and no change in chronic prescription medications for at least 60 days. Changes in medications due to insurance or financial reasons and when within the same class of medications or changes for improvements in medical conditions are not exclusionary. Medications which are taken prn are also no exclusionary.*
4. Expressed interest and availability to fulfill the study requirements
5. For females of child-bearing potential*, must agree to acceptable birth control[&], 4 weeks before enrollment and through 4 weeks after last vaccination.

^{*} *females of child-bearing potential are defined as: not sterilized via tubal ligation, bilateral oophorectomy, salpingectomy, hysterectomy, or successful Essure® placement (permanent, non-surgical, non-hormonal sterilization) with documented radiological confirmation test at least 90 days after the procedure, and still menstruating or <1 year of the last menses if menopausal.*

[&] *acceptable birth control includes: non-male sexual relationships, abstinence from sexual intercourse with a male partner, monogamous relationship with vasectomized partner who has been vasectomized for 180 days or more prior to the subject receiving the first study vaccination, barrier methods such as condoms or diaphragms with spermicide or foam, effective intrauterine devices, NuvaRing®, and licensed hormonal methods such as implants, injectables, or oral contraceptives.*
6. Agrees not to participate in another clinical trial at any time during the study period.
7. Agrees to allow for the indefinite storage of blood samples for future research use.

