1.5 Risks and Potential Benefits

1.5.1 Risks

Risks related to Bivalent or Trivalent vaccine:

Since this is an investigational vaccine and has not been given to humans previously, the risks associated with administration are unknown. These vaccines are killed and purified and will not cause *Salmonella* infection. With an injectable vaccine, recipients may have fever, swelling, redness and pain at the injection site. An allergic reaction, including anaphylaxis, could possibly occur. The Typhoid component of the trivalent vaccine is virtually the same as the licensed vaccine called Typbar-TCV™. This licensed vaccine is known to cause fever in 10% of children who receive it.

Blood Drawing risks:

Blood drawing is sometimes associated with pain at the site from which the blood is drawn, bruising, and occasional lightheadedness and rarely, fainting or infection. Bruising at the site of blood drawing can be prevented by applying pressure for several minutes. To reduce the risk of infection, the area is wiped clean with alcohol and germ-free equipment is used. It is the policy of the American Red Cross that recipients of an experimental vaccine may not be able to donate blood for one year after receipt.

Risks of Confidentiality:

Efforts will be made to keep personal health information confidential. There is a small risk of loss of confidentiality by an unauthorized person viewing study participant records. In order to maintain confidentiality, the PI and the study staff will store study records in a locked area of a limited access locked office. Study records and samples will be coded with a number, not the participant's name. Records will be used by the FDA, the data coordinating center and monitoring group, CVD and the IRB only in connection with carrying out their obligations relating to the study, and every effort will be made to keep the records as confidential as possible, within the limits of the law.

Risks to Pregnancy or Fetus:

If a woman is pregnant or becomes pregnant, this research may hurt the baby or the pregnancy in ways that are unknown. Women of childbearing potential must use birth control to be sure that they do not become pregnant. The only birth control methods that work well enough to be sure that women of childbearing potential will not become pregnant are oral contraceptives ("the pill"), intrauterine devices (IUDs), contraceptive implants under the skin, or contraceptive injections, and condoms with foam.

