5.2 Clinical Laboratory Evaluations

A total of 16 mL blood will be collected for screening clinical labs for the evaluation of eligibility. If screening laboratory results are out of range value, they may be repeated once provided there is an alternative explanation for the out of range value. Participants must have acceptable screening laboratory findings prior to enrollment. The acceptable ranges for study eligibility are listed in Appendix B.

For the assessment of safety, a total of 12.5 mL of blood will be collected for clinical safety labs on Day 1 (pre-vaccination) and the Day 8 (7-days post dose #1) visit. This evaluation is to include a CBC with differential for total white blood cells (WBC) count, hemoglobin (Hg), absolute neutrophil count (ANC), platelet count, creatinine, aspartate aminotransferase (AST),

alanine aminotransferase (ALT), total bilirubin (TBIL), and C-reactive protein (CRP). On Day 2 (one day after receipt of the first dose of vaccine), a 3.5 mL volume of blood will be collected for the assessment of C-reactive protein only. The grading of toxicity for the clinical safety lab values that are not in the normal range is provided in Appendix C.

Due to the U.S. Public Health Emergency with COVID-19, SARS-CoV-2 testing will be performed on the days of scheduled vaccination. These test results are not intended to inform the eligibility of participants for vaccination, as the results are likely to be available after 2-3 days. However, for possible pre-symptomatic participants (i.e., eligible due to the absence of symptoms at the time of vaccination) the positive test result could be used to provide an alternate etiology for the development of symptoms due to COVID-19 rather than due to the study product. The test results of acute infection (positive PCR) or prior infection (positive antibody) will also be used in planned stratified analysis of the immunology outcomes, as COVID-19 infection may alter the immune response to vaccination. The results of SARS-CoV-2 testing will be provided to participants at their Day 7 and Day 36 visits. If SARS-CoV-2 testing results are received prior to these visits, the research team may call participants to report these results.

All women of child-bearing potential will have a serum pregnancy test performed during screening and a urine pregnancy test on the vaccination days. The results of the urine pregnancy test must be negative prior to enrollment in the study, and prior to each vaccination.

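### Read literally, the definition of child-bearing potential leaves a fertile, non-menstruating woman outside the pregnancy tests and contraception rule, and Sections 3.1 and 1.5.1 disagree on three contraceptive methods

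*Combined protocol and SAP*

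**What the plan says.** Inclusion criterion 5 in Section 3.1 applies to females of child-bearing potential, who "must agree to acceptable birth control" from 4 weeks before enrollment to 4 weeks after the last vaccination. A footnote defines the term in two parts joined by *and*. The woman is "not sterilized via tubal ligation, bilateral oophorectomy, salpingectomy, hysterectomy, or successful Essure® placement" (with radiological confirmation), "and still menstruating or <1 year of the last menses if menopausal".

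A second footnote lists the acceptable methods. Among them are "licensed hormonal methods such as implants, injectables, or oral contraceptives". The footnote also names "barrier methods such as condoms or diaphragms with spermicide or foam, effective intrauterine devices, NuvaRing" as acceptable. It further accepts a monogamous relationship with a partner vasectomized at least 180 days before the first vaccination, abstinence, and relationships that do not involve a male partner.

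Section 5.2 sets the testing rule: "All women of child-bearing potential will have a serum pregnancy test performed during screening and a urine pregnancy test on the vaccination days". Exclusion criterion 3 in Section 3.2 and the visit procedures in Sections 6.1 (screening), 6.2 (Day 1) and 6.5 (Day 29, Cohorts C and D) are limited to the same group.

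Section 1.5.1 says the product may harm a pregnancy in unknown ways. It continues: "The only birth control methods that work well enough to be sure that women of childbearing potential will not become pregnant are" the pill, IUDs, implants, injections, and condoms combined with foam.

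**The concern.** The protocol's pregnancy safeguards rest on one defined term, and that term depends on whether the woman is currently menstruating. A woman can be fertile without menstruating, and a missed period is also a common first sign of pregnancy. A rule that uses menstruation to decide who is tested can therefore skip someone the test is meant to find. This is a first-in-human product given twice in some arms, and the protocol itself calls the fetal risk unknown.

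The two method lists raise a second question. If Section 1.5.1 is right that its list is exclusive, the trial admits women on methods it describes as insufficient. If Section 3.1 is right, the risk section is wrong.

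**Working it through.** **Definition.** Write it as A and (B or C), where A is not sterilized, B is still menstruating, and C is menopausal with the last menses less than 1 year ago. Take a woman aged 18–45 (the eligible range) who is not sterilized, not menopausal and without menses:

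- A is true.
- B is false.
- C does not apply, because the 1-year clause is conditional on menopause.
- A and (B or C) is therefore false, and she is not of child-bearing potential.

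**What depends on the term.**

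- Contraception agreement: Section 3.1, criterion 5.
- Exclusion for a positive pregnancy test: Section 3.2, criterion 3.
- General testing rule: Section 5.2.
- Serum test at screening: Section 6.1.
- Urine test on Day 1: Section 6.2.
- Urine test on Day 29, Cohorts C and D: Section 6.5.

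**What might close the gap.** Appendix A marks a pregnancy test at screening and at each vaccination visit without restating the limit. Its laboratory footnote, however, includes β-HCG only where indicated, so it does not extend testing to other women. Exclusion criterion 4 (nursing mothers) removes one cause of absent menses only. Exclusion criterion 15 is discretionary and orders no test.

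**Method lists side by side.**

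| Method | Section 1.5.1 | Section 3.1 |
|---|---|---|
| Oral contraceptives, IUDs, implants, injections | listed | accepted |
| Condoms with foam | listed | accepted |
| Diaphragm with spermicide or foam | absent | accepted |
| NuvaRing | absent | accepted |
| Vasectomized partner | absent | accepted |
| Abstinence, no male partner | absent | accepted (arguably not methods) |

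**Size.** The documents give neither the share of women nor the share without menses. Both figures here are assumptions: half women, and 5–15% without menses.

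- Cohort C has 22 participants (Section 2): 22 × 0.5 = 11 women; 11 × 0.05 = 0.55 and 11 × 0.15 = 1.65.
- If Cohort D (60) also runs: (22 + 60) × 0.5 = 41 women; 41 × 0.05 = 2.05 and 41 × 0.15 = 6.15.

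These counts include placebo recipients. Everyone in Cohort C is injected on both days, but only 6 + 4 = 10 of the 22 are assigned vaccine on both.

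**The case against.** The strongest reply is that the menstrual phrase was meant to separate pre-menopausal from post-menopausal women. Section 3.1 supports this, since it offers implants, injectables and IUDs to women inside the definition and so evidently regards their users as belonging there. Staff may well read it that way and test them. That is plausible and limits the point: a reader might infer that users of hormonal methods are in fact left untested, but the documents do not establish this. They show only that the literal rule permits it. No passage supplies the gentler reading, and Cohort C adds a second site with its own recruitment and consent staff (Section 3, Study Population), so a shared informal reading cannot be taken for granted.

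It is also fair to say that women on an implant, injectable or IUD are already using methods on the Section 1.5.1 list. What they lose is the test and the obligation to continue through 4 weeks after the last dose. That such methods can stop menses is itself an assumption, as the documents do not say so. A woman without menses for another reason loses both safeguards.

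Three stronger readings are not supported:

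- *Several women across the whole trial.* A reader might apply the same assumptions to all 104 participants (52 women; 52 × 0.05 = 2.6, 52 × 0.15 = 7.8). The synopsis's Special Notation describes post-vaccination follow-up of Cohorts A and B as already done, so no wording change reaches their 22 participants. It also says Cohort D may not be conducted.
- *Condoms alone are accepted.* In "barrier methods such as condoms or diaphragms with spermicide or foam" the qualifier can naturally cover both devices, which agrees with Section 1.5.1.
- *The two lists conflict throughout.* Most entries agree, and the disagreement is confined to the additional methods in Section 3.1.

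**Conclusion.** The point holds as a wording defect in a safety rule, with two parts. First, the literal definition lets a non-sterilized, non-menopausal woman without menses go through Day 1 and Day 29 with no pregnancy test and no contraception agreement, and nothing elsewhere in the protocol requires otherwise. Second, the exclusive list in Section 1.5.1 cannot stand beside the longer one in Section 3.1, which adds the diaphragm, NuvaRing and a vasectomized partner.

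The number exposed is small and cannot be derived from the documents: about 0.6 to 1.7 women in Cohort C on the assumptions shown, or about 2.1 to 6.2 if Cohort D runs. The defect itself does not depend on those figures. It depends on reading the footnote as written, and actual site practice is unknown. Sample size, endpoints and analysis are not touched. It should be corrected because the text states a rule that can skip a test and the correction is cheap.

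**What to change.** Reconcile the menstrual condition in the first footnote of Section 3.1 with the birth-control footnote beneath it and with Sections 3.2, 5.2, 6.1, 6.2, 6.5 and Appendix A. Absence of menses alone should not take a non-sterilized, non-menopausal woman out of the tests already scheduled. Reconcile the method lists in Sections 1.5.1 and 3.1 so that they name the same methods. The sponsor's clinical team decides the final definition and which list stands.

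The cost is wording, carried through IRB approval as Section 11.2 requires for any amendment, plus a few extra runs of existing tests. Each added woman in Cohort C would have one serum and two urine tests, so on the same assumptions 3 × 0.55 = 1.65 to 3 × 1.65 = 4.95 runs. The serum test uses the chemistry specimen already drawn (Section 6.1), so no visit or tube is added.

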3.2 Exclusion Criteria

Subjects who meet any of the following criteria at baseline will be excluded from participating in the study:

1. History of typhoid vaccination or known history of typhoid infection within 5 years
2. Unacceptable laboratory abnormality from screening (prior to first vaccination) or upon safety laboratory testing (prior to second vaccination) as listed below. Laboratories with abnormalities which are possibly transient in nature may be repeated one time.
 - a. Hemoglobin, white blood cell (WBC) count, absolute neutrophil count (ANC), or platelet count of an unacceptable value, according to *Appendix B*

- b. Creatinine, AST, ALT, total bilirubin, or C-reactive protein of an unacceptable value, according to *Appendix B*
- c. Positive serology for hepatitis C or HIV antibody or hepatitis B surface antigen.
(Subjects will be informed if their results are positive for hepatitis C, HIV antibody or hepatitis B surface antigen and will be referred to a primary care provider for follow up of these abnormal laboratory tests.)
- 3. For women of child-bearing potential, positive serum pregnancy test (during screening within 45 days of enrollment) or positive urine pregnancy test (prior to and within 24 hours of administering each dose of vaccine).
- 4. Nursing mother.
- 5. Temperature $> 38.0^{\circ}\text{C}$ (100.4°F) or symptoms of an acute self-limited illness such as an upper respiratory infection, including of a COVID-19 infection[#], or gastroenteritis within 10 days prior to each dose of vaccine.
 - # *Symptoms of a COVID-19 infection include fever, chills, cough, shortness of breath or difficulty breathing, fatigue, muscle or body aches, headache, new loss of taste or smell, sore throat, congestion or runny nose, nausea or vomiting, and diarrhea.*
<https://www.cdc.gov/coronavirus/2019-ncov/symptoms-testing/symptoms.html>
- 6. Medical, occupational, or family problems as a result of alcohol or illicit drug use during the past 12 months.
- 7. Diagnosis of schizophrenia or other major psychiatric disease
- 8. Failure to pass *Comprehension Assessment Tool* during screening (70% correct answers are required to pass. Subjects will be provided the opportunity to repeat the test once).
- 9. Receipt of an experimental agent (vaccine, drug, device, etc.) within 28 days before enrollment or expects to receive an experimental agent during the study period.
- 10. Receipt of any licensed vaccine within 2 weeks (for inactivated vaccines) or 4 weeks (for live vaccines) before enrollment in this study.
- 11. Known sensitivity to any ingredient in the study vaccine, including a history of severe allergic reaction to tetanus vaccine.
- 12. Receipt of immunoglobulin or other blood product within the 3 months prior to vaccination in this study.
- 13. Immunosuppression as a result of an underlying illness or treatment with immunosuppressive or cytotoxic drugs, or use of anticancer chemotherapy or radiation therapy within the preceding 36 months.
- 14. Long-term use (>2 weeks) of oral or parenteral steroids (glucocorticoids), or high-dose inhaled steroids (>800 mcg/day of beclomethasone dipropionate or equivalent) within the preceding 6 months (nasal and topical steroids are allowed).
- 15. Other condition that in the opinion of the investigator would jeopardize the safety or rights of a volunteer participating in the trial or would render the subject unable to comply with the protocol.

3.3 Enrollment and Randomization Procedures

Per International Conference on Harmonisation (ICH) guideline E6: Good Clinical Practice (GCP), screening records will be kept at the clinical site to document the reason why an individual was screened, but failed trial entry criteria. The reasons why individuals failed screening will be recorded in the data system.

3.3.1 Re-screening procedure

There may be situations in which a subject is not able to be randomized within 45 days of his/her Screening Visit. In these instances, the subject may need to be re-screened including re-consent. This will involve undergoing all screening procedures again.

Study participants that meet all inclusion and exclusion criteria and have signed the informed consent form will be assigned a subject identification number. A randomization code will be prepared by a CVD statistician and will determine the blinded assignment of each subject to a treatment arm. A designated independent individual (e.g., Independent Safety Monitor) will be provided with a back-up randomization code list for emergency unblinding purposes and which will be maintained in a secure location.

Subjects, investigators, and study personnel performing any study-related assessments following study vaccine administration will be blinded to subject treatment assignment. Laboratory personnel performing the immunogenicity assessments will also remain blinded to subject treatment assignment.

